Statistical Issues: In our pilot study, we were able to collect useable data from five of the eleven subjects that were enrolled (45%). In the five subjects that produced usable results, the signal of interest had a mean value of -3.764×10^{-7} Moles with a standard deviation of 2.135×10^{-7} Moles. This results in a standardized effect size of 1.763, when using a zero mean for the null case. In order to achieve a 90% power level for this measure, the number of usable data sets is therefore eight. Considering our previous success rate of 45%, approximately 18 subjects will need to be enrolled into each group of the study for a total enrollment of 54 subjects. The data analysis will first be performed on a within-subject basis. Then, the original raw optical time series will be averaged across subjects (for corresponding optode placements only, standardized relative to the EEG 10-20 system).

1. Specific Aims /Objectives

The primary aim is to utilize near-infrared spectroscopy (NIRS) in patients under general anesthesia to measure hemodynamic activations in the bilateral somatosensory cortices and the prefrontal cortices in response to the noxious stimulation (pain) associated with catheter ablation of arrhythmias. Randomization of patients to placebo or one of two opioid doses should allow for discrimination between cortical activation and scalp sympathetic changes in response to pain.

Secondary aims are to utilize NIRS to measure hemodynamic activation in the supplemental motor area to actual or intended movement either spontaneously or in response to pain, and in the auditory cortices in response to auditory stimuli.

This study is part of an ongoing project to determine the value of NIRS as a tool for measurement of pain during general anesthesia and to monitor depth of anesthesia in order to prevent awareness.

2. Background and Significance

Anesthesia is a state of drug-induced unconsciousness with suppression of sensory perception, differing from normal sleep by the intensity of stimulus required to awaken the brain to conscious perception. Anesthesia can be defined by hypnotic (unconsciousness) and analgesic (pain relief) components, so that clinical anesthesia involves the administration of hypnotic and analgesic agents with the anesthesiologist observing the clinical response to noxious stimuli and adjusting the dosage to achieve an adequate depth of anesthesia.

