is capable of continuously monitoring and tomographically imaging changes in oxy-and deoxyhemoglobin concentrations during somatosensory stimulation, such as finger tapping, finger tactile, and electrical median nerve stimulation (Becerra, Harris et al. 2008, Minati, Jones et al. 2009, Nambu, Osu et al. 2009) and multiple applications in children (Wolf and Greisen 2009, Watanabe, Homae et al. 2010). We have also shown with fMRI studies that pain stimulation activates sensory areas. Our group has a great deal of experience performing DOI measurements simultaneously with fMRI, and have demonstrated that the functional signals measured with DOI correlate temporally with fMRI signals (Strangman, Culver et al. 2002).

In our previous work using the same approach we have shown that an acute thermal stimulus using an FDA-approved Peltier thermode produces significant and measurable effects that can be measured in a number of cortical regions in healthy volunteers (Becerra, Harris et al. 2008). We have not completed the work on simultaneous fMRI and DOT measures in healthy subjects and this continues under an approved IRB protocol at MGH, 2007-P-000270, entitled “Assessing the Cortical Response to Painful Stimuli with Diffuse Optical Imaging”.

4. Design and Methods

a. Study Design

General Procedures

We plan to study and obtain useful data sets in 45 subjects (12-30 years of age) scheduled for elective electrophysiology procedures in the cardiac catheterization laboratory and undergoing ablation of arrhythmias under planned general endotracheal anesthesia. As a number of subjects may choose to withdraw from the study following enrollment, and because some subjects will not be able to participate in the study if it is not possible to obtain adequate NIRS signals (as discussed below under Study Procedure: Day of Surgery), we plan to enroll 54 subjects to allow for drop-outs.

- **Pre-Operative Visit**

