Prior to the induction of general anesthesia, we will perform the following to test optode placement and signal quality:

1. Resting state data will be collected for about 200 seconds while the patient is quietly lying still. This baseline data will be used to compare changes observed during the catheterization procedure.
2. Auditory Stimuli: Headphones will be placed on the subject's head and an audio recording will be presented to the subjects. This data will be used as baseline consciousness data, as well as to familiarize the subject with the study procedures. In order to activate the Supplemental Motor Area (SMA), which should be quiet unless patients move, we will adapt a previously employed method for evaluating subjects in the vegetative state (Owen, Coleman et al. 2006). The auditory stimulus will be presented for 5 seconds, with a varied inter-stimulus interval. The prompt will request that the subject imagine squeezing a tennis ball in their right hand in a clasping motion, without actually performing the action. During this we expect SMA activity to occur if the subject is consciously aware.
3. . The subject will be asked to perform a brief finger tapping exercise, tapping the fingers of the left hand against the thumb for 5 seconds, with 15 seconds between, for 5 cycles. This will only be conducted if time permits.
4. . Brush stimuli will be applied to the dorsum of the left hand in a similar manner. This will only be conducted if time permits.

4.

A BIS (Bispectral Index) monitor will be used in all study patients in order to control the depth of anesthesia. A BIS sensor will be placed on the forehead and a BIS value between 40 and 60 will be targeted. A BIS <60 is advocated to prevent awareness during general anesthesia (Avidan, Zhang et al. 2008). This will also allow for reduced variability in the depth of anesthesia between the subjects during the ablations.

During the Procedure:

The audio stimuli will be presented to the subject every half hour throughout the procedure. Near-infrared signals are measured and recorded by the NIRS device (TechEn CW 7) throughout the procedure and will not influence the procedure.

The anesthetic technique will be standardized for all study subjects, and will comprise the following:

Premedication: Midazolam 0.05 mg/kg IV up to a maximum of 2 mg
Induction: Fentanyl 1.5 mcg/kg IV up to a maximum of 3 mcg/kg. No fentanyl after induction.
Propofol – standard dosage titrated to effect

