The only substantive difference between the study protocol and standard clinical care is the administration of remifentanil. Intravenous opioids are typically not given beyond induction of general anesthesia nor during catheter ablation of the arrhythmia.

e. Definition of Primary and Secondary Outcomes/Endpoints

Primary Outcomes:

The primary outcome is the use of NIRS to measure/detect hemodynamic activations in the bilateral somatosensory cortices and the prefrontal cortices in response to the noxious stimulation

(pain) associated with catheter ablation of arrhythmias, and whether these activations are reduced or eliminated by remifentanil.

Secondary Outcome:

The secondary outcome is the use of NIRS to measure hemodynamic activation in the supplemental motor area to actual or intended movement either spontaneously, in response to pain, and/or in response to auditory stimuli.

f. Data Collection Methods, Assessments and Schedule (what assessments performed, how often)

The study will consist of enrollment and a Preoperative Questionnaire at the pre-catheterization work-up, the study protocol during two days if the patient is discharged the same day of the procedure, or three days if the subject is admitted overnight.

Prior to Preoperative Visit:

- Assessment of eligibility criteria

Pre-Operative Visit:

- Presentation of research study, informed consent/assent (20 minutes)
- Preoperative Questionnaire if patient/parents consent/assent (10 minutes)

Day of Procedure:

1) Before Procedure

- Equipment setup (20 minutes). Test run of brush and audio stimuli (10 minutes).
- BIS sensor applied to patient.

2) During Procedure

- Infusion of NaCL or remifentanil started after induction of anesthesia.
- Audio stimuli (5 seconds each) presented to the patient every half an hour.
- Electronic anesthesia record will capture relevant anesthetic and physiologic data. Study Coordinator and/or Research Nurse will document time and duration of ablations, times of catheter insertion and removal, and assure safety of the patient
- An investigator will operate the NIRS equipment.
- NIRS cap with optodes will be removed from the patient just prior to emergence from anesthesia.
- Average duration of an electrophysiologic study with catheter ablation of arrhythmias is 3 to 4 hours.

3) After Procedure

- Postoperative Questionnaire (10 minutes) will be administered before subject is discharged from the hospital, either on the day of or day following the procedure.

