The NIRS instrument will acquire raw data from each detector at ~40 kHz. The individual signals will then be bandpass filtered. Next, the time series pairs from each detector will be converted from wavelength (absorption) to relative concentrations (of oxy-/deoxy-hemoglobin). This will be done with the modified Beer-Lambert Law and the absorption coefficients of oxy- and deoxy-hemoglobin (HbO and Hb, respectively). (The near-IR wavelengths are chosen because oxy-/deoxy-Hb are the predominant absorbers in the tissue at these wavelengths.) The result will be an oxy-Hb and deoxy-Hb time series associated with each source-detector pair.

For each stimulation run, each smoothed oxy-/deoxy-hemoglobin time series will be examined for periodic amplitude fluctuations. Expected fluctuations include heart rate (~1-3 Hz), breathing and/or “v-waves” (~0.1Hz), as well as any fluctuations induced by the experimental paradigm. If the former sources of noise are substantial, an attempt will be made to filter out these fluctuations (in Fourier space). Any analysis of filtered data will be compared to an analysis of the corresponding non-filtered data. The oxy-hemoglobin portion of the experimentally-induced changes are expected to be 4-9 sec out of phase with the paradigm onsets and offsets (as seen in fMRI work as well as in prior optical recordings).

The data analysis will first be performed on a within-subject basis. Then, the original raw optical time series will be averaged across subjects (for corresponding optode placements only, standardized relative to the EEG 10-20 system).

The biological basis for the signals measured by the optical technique is the same as the basis for fMRI and PET scanning. The regions to be sampled in these pilot studies will be several times larger than single voxels in fMRI scanning. Furthermore, experiments with similar optical instruments indicate that these instruments are at least as sensitive as fMRI. With larger sampling regions (up to a factor of 5 or more), and assuming only comparable sensitivity, the optical imaging should require no more subjects than an fMRI study, and perhaps fewer. Furthermore, optical recording can provide 10-100 times the temporal resolution of fMRI. So, since an optical time series would seem to be at least as good as that coming from an individual voxel (or small collections of voxels) from fMRI data, similar group sizes should be adequate for optical experiments (Boas, Dale et al. 2004).

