d. Statistical Power and Sample Considerations

In our pilot study, we were able to collect useable data from five of the eleven subjects that were enrolled (45%). In the five subjects that produced usable results, the signal of interest had a mean value of -3.764×10^{-7} Moles with a standard deviation of 2.135×10^{-7} Moles. This results in a standardized effect size of 1.763, when using a zero mean for the null case. In order to achieve a 90% power level for this measure, the number of usable data sets is therefore eight. Considering our previous success rate of 45%, approximately 18 subjects will need to be enrolled into each group of the study for a total enrollment of 54 subjects.

e. Study Organization

The principal investigator for this study is [name], MBBCh in the Department of Anesthesiology, Perioperative and Pain Medicine at Boston Children’s Hospital. The Research Nurse(s), Study Coordinator ([name] MPH), and co-investigators ([name] MD, and [name] PhD) are members of the Department of Anesthesiology, Perioperative and Pain Medicine at Boston Children’s Hospital. Other co-investigators ([name] MD) and ([name] PhD) are members of the Department of Cardiology at Boston Children’s Hospital and Martinos Center for Biomedical Imaging, Department of Radiology, Massachusetts General Hospital), respectively. Members of the P.A.I.N. research group will participate in data collection and data analysis.

f. Data and Safety Monitoring Plan

Confidentiality will be ensured by assigning anonymous subject identification codes to each subject. The subject-screening log, which lists the names corresponding to the subject identification codes, will be kept on a locked computer, access to which is limited to only one investigator.

The risk posed to the subject in this study is minimal. Subjects will have the right to discontinue the study at any time prior to induction for any reason. Also, investigators will be in the room ready to stop the experiment in case there is any sort of adverse event. After induction of anesthesia the attending anesthesiologist and/or cardiologist may discontinue the experiment if clinical conditions warrant or in the case of an adverse event. Adverse events will be reported to the IRB as indicated above.

The investigators will review the data after the first 5 subjects and then after every 10 subjects to ensure that adequate data is being obtained.

6. Risks and Discomforts

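### The only group-level step in the Data Analysis Plan averages raw optical series across subjects, which by itself cannot answer either part of the primary outcome

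*Combined protocol and SAP*

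**What the plan says.** Section 4.e sets a primary outcome in two parts. The first is detection: "The primary outcome is the use of NIRS to measure/detect hemodynamic activations in the bilateral somatosensory cortices and the prefrontal cortices", in response to ablation. The second is "whether these activations are reduced or eliminated by remifentanil". Section 1 rests the design on the randomised comparison: "Randomization of patients to placebo or one of two opioid doses should allow for discrimination between cortical activation and scalp sympathetic changes".

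Section 5.c covers filtering, conversion to oxy- and deoxyhemoglobin, and inspection for periodic noise. It says that analysis starts within each subject, and then gives its one group-level step: "Then, the original raw optical time series will be averaged across subjects", for matching optode positions. The Statistical Issues paragraph of the opening summary repeats this. Neither place names a per-subject response value, a time window, an error term, a test, a model, an alpha or a comparison of arms.

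Section 5.d gives a pilot mean and SD over five usable subjects and a standardised effect of 1.763, "when using a zero mean for the null case". It concludes: "In order to achieve a 90% power level for this measure, the number of usable data sets is therefore eight". It names no test and no alpha.

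**The concern.** A series averaged within an arm is one curve per arm. Unless the spread between subjects is carried along with it, the curve cannot show whether a response differs from zero or whether two arms differ by more than subject-to-subject variation would produce. The plan does not say that the spread is carried along, or that the averaging is done by arm. The step also returns to the original raw optical series, although 5.c has by then converted the data to the hemoglobin concentrations that the study sets out to measure.

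At stake is the primary conclusion. If the plan is followed as far as it is written, an apparent remifentanil effect, or its absence, would have no standard error or confidence interval. The team would have to choose the response window, region, chromophore and test later, with no pre-stated choice to hold to.

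**Working it through.** **Inputs.** From 5.d: pilot mean −3.764×10⁻⁷ (size used below), SD 2.135×10⁻⁷, 5 usable subjects, 90% power, 8 usable data sets, 45% usable rate, 18 enrolled per group, 54 in total. From 4.a: "We plan to study and obtain useful data sets in 45 subjects", or 45/3 = 15 per arm if equal. Assumed, because not stated: t tests, two-sided alpha.

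**1. The plan's own figure.** d = 3.764/2.135 = 1.763. Enrolment: 8/0.45 = 17.8, rounded up to 18; 3 × 18 = 54. These reproduce.

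**2. Which test gives eight?** Power is from the noncentral t, with noncentrality d√(n/2) on 2n − 2 df for two samples and d√n on n − 1 df for one sample.

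| Test | n = 6 | n = 7 | n = 8 | Smallest n for 90% |
|---|---|---|---|---|
| Two-sample, two-sided 0.05 | 0.786 | 0.857 | 0.906 | 8 |
| One-sample against zero, two-sided 0.05 | 0.927 | 0.970 | 0.988 | 6 |
| One-sample against zero, two-sided 0.05/3 | 0.745 | 0.865 | 0.934 | 8 |

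Two different tests give exactly eight, so the number does not identify the intended analysis. Every version needs one value per subject and the SD between subjects. An averaged series supplies neither.

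**3. What a subject-level analysis would deliver at 8 usable per arm.** Assume the pilot mean and SD in each arm, two-sided 0.05 and no multiplicity adjustment. For a dose that removes a fraction r of the response, the noncentrality is r × 1.763 × √(8/2) = 3.526r on 14 df.
- Full elimination (r = 1): 0.906. A 50% reduction (r = 0.5): 0.376.
- Placebo response against zero (one-sample, 7 df): 0.988.
- 95% half-width for an arm difference: 2.145 × 2.135×10⁻⁷ × √(2/8) = 2.29×10⁻⁷, which is 61% of the pilot response.
- 95% half-width for the response in one arm: 2.365 × 2.135×10⁻⁷/√8 = 1.78×10⁻⁷, or 47%.
- With 15 per arm, power is 0.997 for full elimination and 0.645 for a 50% reduction.

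**4. Range from the pilot SD.** Under normality with 4 df, the 95% interval for the SD runs from 2.135√(4/11.143) = 1.28 to 2.135√(4/0.4844) = 6.14 (×10⁻⁷). With the mean held at 3.764×10⁻⁷, d runs from 2.94 down to 0.61. At 8 per arm:

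| SD (×10⁻⁷) | Full elimination | 50% reduction |
|---|---|---|
| 1.28 | over 99% | 78% |
| 2.135 | 91% | 38% |
| 6.14 | 21% | 9% |

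**The case against.** The strongest reply is that this is silence rather than a faulty method. The plan analyses within subject first, averaging does not delete those results, and an SD across subjects can be reported beside any mean. Section 5.d uses a between-subject SD and a power target, so the authors evidently had a subject-level test in mind. Much of this stands: the data can support the right analysis, and one may well be intended. But a power statement is not an analysis method. It refers only to a zero-mean null and does not define the contrast between doses and placebo. The per-subject windowed means in the Figure 1 legend (section 2) belong to an earlier study. The one step that is written does not do what 4.e asks.

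Some stronger readings are tempting but not supported:
- A reader might infer that eight is the wrong number, or that it must come from a two-sample test. The table in the working shows that it does not settle the test, and no error in eight is shown.
- A reader might infer that the arms will be merged, or curves judged by eye. The documents say neither, and they give no rule for declaring an effect from the size of a gap between curves.
- A reader might take the resting recording made before induction as the sole reference for the ablation response, since 4.a says "This baseline data will be used to compare changes observed during the catheterization procedure". The same section gives those tests a signal-quality purpose, and 5.c ties the response to paradigm onsets and offsets. No harm to the randomised comparison is shown.

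**Conclusion.** The point holds in this form: the only stated group-level step, taken by itself, supplies no between-subject error and no comparison of arms. It therefore cannot answer either part of the primary outcome, and it does not match the subject-level basis of the sample size. It should be fixed. This conclusion rests on the text alone.

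The power figures illustrate what a replacement analysis could deliver; they are not evidence of an error in 5.d. They assume the five-subject pilot mean and SD in each arm, normality, 8 usable per arm and no multiplicity adjustment. On those terms the design is well powered for full elimination by a dose (91%) and weak for a 50% reduction (38%). The uncertainty in the pilot SD is too wide for either figure to be quoted without its range.

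**What to change.** In 5.c and the Statistical Issues paragraph, replace the averaging step as the basis for inference.
- **Value per subject.** Use the converted oxy- and deoxyhemoglobin data: the mean in a post-onset window minus the mean in a window just before each ablation, averaged over that subject's ablations. Fix the windows and the primary region and chromophore before group codes are released.
- **Tests.** Test the placebo-arm response against zero, and each remifentanil arm against placebo, with between-subject error. State the alpha and a multiplicity rule for the two doses; Holm is one suitable choice.
- **Regions.** Section 4.e lists several. Either name one in advance as primary or cover them with a multiplicity rule.
- **Reporting.** Give arm differences with 95% confidence intervals. For elimination, give the response remaining in each remifentanil arm with its interval, because a non-significant test does not show absence.
- **Averaged curves.** Keep them as descriptive figures.
- **Section 5.d.** Name the test and alpha behind eight, and add power for partial reduction with its range.

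No new measurement is needed: NIRS is recorded throughout the procedure (4.a) and staff log ablation times and durations (4.f). The costs are modest analysis work and alignment of the logged times with the NIRS record, closely enough for a response that 5.c expects 4 to 9 seconds from onset. The power statement for partial reduction also becomes less favourable, and a multiplicity adjustment lowers it further.
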